MRI scans may be used instead of CT scans for imaging of the abdomen and pelvis. However, the chest must be imaged using CT; and chest disease must be followed by CT scan (ie, chest x-ray for response assessment is not allowed). The same method of assessment used during Screening must be used at all subsequent time points. If iodinated intravenous contrast is contraindicated, chest CT scan should be performed without intravenous contrast.

A brain scan should be performed for all subjects to assess potential central nervous system disease and/or metastases as clinically indicated. For eligible subjects with previously treated brain metastases, a brain scan will be required at all tumor assessment time points (eg, every 6 weeks). For all subjects, a follow-up brain scan must be performed to confirm a complete response (CR) within 1 week following response confirmation.

The first radiological assessment of tumor response status will be performed during Week 6, unless there is clinical indication warranting earlier radiologic imaging. Response assessments will be repeated every 6 weeks until disease progression as determined by the investigator. Although clinical progression may be determined by the investigator based upon clinical deterioration, every effort should be made to document progression using radiographic methods. Signs and symptoms of clinical deterioration that lead to disease progression should be documented.

Subjects discontinued from treatment without disease progression will continue to undergo tumor assessments every 6 weeks until documented disease progression or initiation of another anticancer therapy.

Subjects who discontinue study treatment, regardless of their reasons for doing so, will be followed for survival approximately every 12 weeks for up to 12 months or until 6 cycles after last patient in, death, loss to follow-up, or withdrawal of consent, whichever occurs first.

Pharmacokinetic Assessments

Plasma samples for PK analyses will be collected during C1 on Day 1, Day 8, and Day 15 in Part 1, Dose Escalation. Plasma samples for PK analyses will be collected during C1 on Day 8, and Day 15 in Part 2, Expansion, according to the Schedule of Assessments.

Urine and plasma samples for assessment of the metabolite profile will be collected during C1 on Day 8 for urine and Day 1, Day 8, and Day 15 for plasma in Part 1, Dose Escalation, only.

During the Expansion phase, H3B-6527 levels in tumor tissue may be analyzed. During Dose Escalation, the investigators and Sponsor may agree that determination of H3B-6527 exposure in tumor tissue is required to guide decisions pertaining to drug administration. In this scenario, biopsies of tumor tissue will be obtained from all consenting subjects.

Pharmacodynamics, Pharmacogenomics, and Other Biomarker Assessments

Pharmacodynamics biomarkers including biomarkers to show target engagement and impact of H3B-6527 treatment on disease will be evaluated from collected samples as outlined in the schedule of assessments. Retrospective testing for potential subject stratification markers will also be explored. Results from biomarker studies may be used to aid the selection of the RP2D and schedule, and for monitoring drug efficacy. When new research results emerge, the parameters and methods for the pharmacodynamic biomarker analysis may change.

Biomarker Sample Collection

Screening Phase biomarkers:

Subjects in the Dose Expansion phase will be evaluated for FGF19 expression. A fresh tumor biopsy (for determining FGF19 expression levels by a Sponsor designated laboratory), the signing of the ICF, and the collection of blood samples for pharmacodynamic analysis (same day as fresh tumor biopsy) will be required up to 8 weeks before administration of H3B-6527 on C1 Day 1, in order to enroll in the Dose Expansion Phase of the study. The 28-day Screening Period will begin when any of the remaining screening assessments are performed. The entire Pretreatment Phase must be completed within 8 weeks of study drug administration on C1 Day 1. Archived, fixed tumor tissue is also to be collected (if available) for all consenting subjects in both the Dose Escalation and Expansion phases. These tissues and peripheral blood samples (for both Dose Escalation and Dose Expansion phase) may be used for assessment of mutations and other exploratory biomarkers.

Baseline and Treatment Phase Biomarkers:

Blood (serum/plasma) biomarker samples from study subjects may be analyzed for FGF19 (ligand of H3B-6527's target FGFR4), bile acids, circulating tumor cells and other exploratory biomarker candidates (both protein and nucleic acids) using global proteomic/metabolomics/genomic methods, enzyme-linked immunosorbent assay, multiplex bead-based immunoassay, or other assays/methods. These blood biomarker samples may be used for exploratory analysis for evaluation of response-related and/or safety-related outcomes as well as for potential use in diagnostic development.

In the event a subject is required to have a repeat tumor biopsy for medically indicated reasons, freshly obtained biopsy tissue from the procedure should be collected and shipped to H3 Biomedicine, Inc., or a predesignated laboratory for exploratory biomarker analysis as outlined in the laboratory manual.

Pharmacogenomics Assessment

A blood sample will be collected for pharmacogenomic (PG) analysis. The role of deoxyribonucleic acid (DNA) sequence variability on the absorption, distribution, metabolism, and elimination (ADME) of H3B-6527 may be evaluated in this study. Variation in H3B-6527 exposure or the occurrence of AEs observed in the study population may be evaluated by correlation of single-nucleotide polymorphisms with PK, safety, or pharmacodynamic data. Genomic DNA extracted from blood samples may be used to confirm whether the DNA sequence variants observed in DNA extracted from tumor material are limited to the tumor.

Data obtained will be used for research, to assist in developing safer and more effective treatments, and will not be used to change the diagnosis of the subject or alter the therapy of the subject. The

DNA will not be used to determine or predict risks for diseases that an individual subject does not currently have. Any sample or derivatives (DNA, ribonucleic acid, and protein) may be stored for up to 15 years to assist in any research scientific questions related to H3B-6527 or cancer and for potential diagnostic development.

General

Archived tumor tissue samples and blood samples for pharmacodynamic, PG, and other biomarker assessments will be collected from all consented study subjects, except where prohibited by regional or local laws. Samples will be collected at designated time points as specified in the Schedule of Procedures/Assessments.

Samples may be used for biomarker discovery and/or validation to identify blood or tumor biomarkers that may be useful to predict treatment response (efficacy, pharmacodynamics), PK, and/or safety-related outcomes. Samples may also be used for potential diagnostic development. In addition, biomarkers identified in other clinical studies may also be assessed in samples collected from subjects enrolled in this study. The decision to perform exploratory biomarker analysis will be based on the clinical outcome of the study, the signals observed in other clinical studies and/or the scientific rationale of the study.

Instructions for the processing, storage, and shipping of samples will be provided in the Laboratory Manual.

Safety Assessments

Safety assessments include monitoring and recording all AEs, including serious adverse events (SAEs); clinical laboratory tests (including hematology, coagulation parameters, clinical chemistry (including total bile acids, cholesterol, triglycerides), and urinalysis; and periodic measurement of vital signs, ECGs, MUGA scans/echocardiograms, ophthalmic and physical examinations.

Additionally, QTc intervals will be evaluated during Dose-Escalation. All AEs will be assessed using the National Cancer Institute CTCAE, Version 4.03.

Bioanalytical Methods

Plasma concentrations of H3B-6527 will be determined using a validated assay. If appropriate, assessment of plasma and urine samples for any metabolites of H3B-6527 may be explored.

The ability to determine tumor concentrations of H3B-6527 may be explored using a nonvalidated assay such as matrix-assisted laser desorption/ionization.

Statistical Methods

Primary Endpoints

- Occurrence of DLTs as a function of the dose of H3B-6527 for determination of the MTD and RP2D.
- Safety/tolerability: the type and frequency of AEs, SAEs using CTCAE, Version 4.03, as well as changes in clinical laboratory values, ECG parameters and vital sign measurements.

Secondary Endpoints

- PK: Standard primary PK parameters including but not limited to the area under the plasma concentration-time curve from time 0 through the last measurable point (AUC_{0-t}), maximum observed plasma concentration (C_{max}) and time of maximum observed plasma concentration (t_{max}).

- Preliminary antitumor activity: Response will be determined by the investigator using mRECIST. The following endpoints will be determined:
 - Objective response rate (ORR), defined as the proportion of subjects achieving a best overall response of partial response (PR) or CR (PR + CR), from first dose date until disease progression/recurrence.
 - Duration of response, defined as the time from the date of first documented CR/PR until the first documentation of disease progression as determined by the investigator or death, whichever comes first.
 - Progression-free survival (PFS), defined as the time from first dose date to the date of the first documentation of disease progression as determined by the investigator or death (whichever occurs first).
 - Overall survival (OS), defined as the time from first dose date to the date of death.
 - Time to response, defined as the time from first dose date to the date of first documented CR/PR.

Exploratory Endpoints

- Correlation of biomarker expression levels with antitumor activity and safety
- Expression levels of biomarkers in blood and tumor samples
- Correlation of biomarker expression levels with H3B-6527 exposure in plasma
- H3B-6527 levels in tumor tissue may be assessed
- H3B-6527 metabolites in plasma and urine.

Analysis Sets

Full Analysis Set will include all subjects who received at least 1 dose of study drug. This will be the primary analysis set for efficacy evaluations, as well as for demographic and baseline characteristics. The summary of efficacy will be based on this set for HCC subjects.

Safety Analysis Set will include all subjects who received at least 1 dose of the study drug. This will be the analysis set for all safety evaluations except DLT results.

PK Analysis Set will include all subjects who have received at least 1 dose of study drug and have at least 1 evaluable plasma concentrations.

Pharmacodynamics Analysis Set will include all subjects who have received at least 1 dose of study drug and have evaluable pharmacodynamic data.

PK/Pharmacodynamics Analysis Set will consist of all subjects in the Safety Analysis Set that also have evaluable plasma PK and pharmacodynamic pretreatment assessment and at least 1 post treatment assessment.

Response Evaluable Set will consist of those HCC subjects who have received at least 1 dose of study drug and have measurable disease at baseline and at least 1 postbaseline evaluation.

Efficacy Analyses

ORR, response duration, time to response, PFS, and OS will be listed and descriptively summarized as appropriate.

- **Response duration and time to response:** Summary statistics (median Q1, Q3 and range)

will be generated on subjects achieving a best overall response of PR or CR (PR + CR).

PFS and OS: The PFS censoring rules will follow the Food and Drug Administration guidance. PFS will be reported in both summary tables and plotted with Kaplan-Meier curve. Time of death will be censored for subjects who are without death information at the time of OS analysis. OS will be reported in both summary tables and plotted with Kaplan-Meier curve.

Pharmacokinetic Analyses

Plasma concentrations of H3B-6527 will be tabulated and summarized by dose level, day, and time. H3B-6527 PK parameters will be derived from plasma concentrations by noncompartmental analysis using actual times. Minimally, the following PK parameters will be calculated: C_{max} , t_{max} , AUC_{0-t} , accumulation ratio (R_{acc}); and if data permit, area under the plasma concentration-time curve extrapolated to infinity (AUC_{0-inf}), terminal elimination half-life ($t_{1/2}$), apparent total body clearance (CL/F), and apparent volume of distribution during the terminal phase (V_z/F).

Pharmacodynamics, Pharmacogenomics, and Other Biomarker Analyses

Pharmacodynamics, PG and other biomarker analyses may be performed and reported separately. Details of these analyses will be described in a separate analysis plan.

Safety Analyses

Evaluation of safety will be performed on the Safety Analysis Set. Safety data to be evaluated include AEs, clinical laboratory results, vital signs, ECGs, and the results of ophthalmic and physical examinations.

Safety parameters will be summarized using descriptive statistics (mean, standard deviation, median, Q1, Q3, and range for continuous variables; numbers and percentages for categorical measures).

The effects of H3B-6527 on cardiovascular repolarization will be evaluated via 12-lead continuous Holter/ECG monitoring on C1 Day 1 and Day 8 in the Dose Escalation phase of the study only. Individual ECGs will be extracted from the Holter recordings at specified time points per ECG manual and will be evaluated by a central laboratory. QT intervals will be measured from Lead II and will be corrected for heart rate using Fridericia's formula (QTcF) correction factor. The primary QTc parameter will be QTcF. Secondary parameters (QT corrected for heart rate using Bazett's formula [QTcB], QT, PR, QRS, and heart rate) and waveforms (T waves) will be evaluated.

Interim Analyses

There is no formal interim analysis for efficacy. There will be an interim analysis to define the MTD and/or RP2D prior to initiating the Expansion phase of the study. Other interim analyses may be performed to determine if a different dose schedule (eg, BID) or frequency (eg, 2 weeks on/1-week off) may be preferable. Safety and PK summaries may be provided periodically.

Sample Size Rationale

Dose Escalation phase (Part 1)

It is anticipated that selection of the RP2D will be based on an integrated evaluation of safety, tolerability, clinical benefit, PK, and pharmacodynamic data. The total number of subjects to be enrolled is dependent upon the observed safety profile, which will determine the number of subjects per dose cohort, as well as the number of dose escalations required to achieve the MTD of H3B-6527 and establish the RP2D. For each dose schedule of QD and BID, assuming 5 dose levels for QD dose schedule and 3 dose levels for the BID dose

schedule will be studied and a maximum of 6 subjects will be enrolled per dose level, then between 30 to 48 subjects may be accrued during dose escalation.

Dose Expansion phase (Part 2)

Prior to starting the Dose Expansion phase, the investigators and the Sponsor will use safety, efficacy, PK, and pharmacodynamic data obtained during the Dose Escalation Phase, as well as clinical judgement, to jointly determine the dose schedules to be studied.

During Part 2, the Dose Expansion phase, a sample size of 40 evaluable subjects per dose schedule will be enrolled to examine QD and/or BID dosing of H3B-6527 based on the recommended dose determined from Part 1. For a reference of the precision of ORR estimates, the associated 2-sided 95% CIs for ORR up to 30% for 40 subjects are provided. This study makes provision for exploring a BID schedule of H3B-6527 during the Dose Expansion phase if evaluation of the PK, pharmacodynamics, or safety of H3B-6527 suggests that it may be preferable to administer H3B-6527 BID rather than QD. When both dose schedules are accruing subjects, an alternating enrollment schema into QD and BID dose schedules will be followed.

Treatment Arms for Part 2, Dose Expansion

Treatment Arm	Number of Subjects
1: Subjects with advanced HCC who are FGF19-positive to receive H3B-6527 QD for 21-day cycles	40 subjects
2: Subjects with advanced HCC who are FGF19-positive to receive H3B-6527 BID for 21-day cycles	40 subjects

BID = twice daily, HCC = hepatocellular carcinoma.

2-sided 95% Confidence Interval for ORR Estimate Up to 30% (40 subjects)

ORR (N=40)	2-sided 95% CI
5% (2 responders in 40 subjects)	(0.006, 0.169)
7.5% (3 responders in 40 subjects)	(0.016, 0.204)
10% (4 responders in 40 subjects)	(0.028, 0.234)
12.5% (5 responders in 40 subjects)	(0.042, 0.268)
15% (6 responders in 40 subjects)	(0.057, 0.298)
17.5% (7 responders in 40 subjects)	(0.073, 0.328)
20% (8 responders in 40 subjects)	(0.091, 0.356)
22.5% (9 responders in 40 subjects)	(0.108, 0.385)
25% (10 responders in 40 subjects)	(0.127, 0.412)
27.5% (11 responders in 40 subjects)	(0.146, 0.439)
30% (12 responders in 40 subjects)	(0.166, 0.465)

CI = confidence interval, ORR = objective response rate.

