During Part 2, the Dose Expansion phase, a sample size of 40 evaluable subjects per dose schedule will be enrolled to examine QD and/or BID dosing of H3B-6527 based on the recommended dose determined from Part 1. For a reference of the precision of ORR estimates, the associated 2-sided 95% CIs for ORR up to 30% for 40 subjects are provided. Subjects enrolled into Part 2, Dose Expansion phase, must be FGF19-positive as defined by Sponsor-designated laboratory.

When both dose schedules are accruing subjects, an alternating enrollment schema into QD and BID dose schedule will be followed.

Study Phases

The study will be conducted in the following 4 phases: Pretreatment Phase, Treatment Phase, Extension Phase, and Follow-up Phase.

Pretreatment Phase

This Pretreatment Phase will last no longer than 28 days and includes:

- **A Screening Period** to establish protocol eligibility.
- **A Baseline Period** to establish disease characteristics before treatment.

Treatment Phase

The Treatment Phase will last for 1 treatment cycle of 21 days.

Subjects who are receiving study drug at the end of the Treatment Phase will continue to receive study drug in the Extension Phase.

Extension Phase

In the Extension Phase, subjects will continue to receive the same treatment and dose they received during the Treatment Phase, provided termination criteria are not met.

Treatment and Extension Phases

Subjects will discontinue study drug at the time of disease progression, development of unacceptable toxicity, withdrawal of consent, or termination of the study by the Sponsor. However, subjects may continue to receive study treatment as long as they demonstrate clinical benefit as judged by the investigator after discussion with the Sponsor or until the end of the study. Disease progression will be determined by the investigator following relevant modified Response Evaluation Criteria in Solid

Tumors (mRECIST) guidelines. The mRECIST for this protocol harmonizes the original mRECIST criteria ([Lencioni and Llovet, 2010](#)) using triphasic liver computed tomography (CT)/magnetic resonance imaging (MRI; optimized for precontrast, arterial phase, and portal venous phase) and elements of Response Evaluation Criteria in Solid Tumors, Version 1.1 ([Eisenhauer, et al., 2009](#)).

Follow-up Phase

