### 5.4.1 Analysis of Efficacy Endpoints Based on Tumor Response

ORR, duration of response (DOR), time to response and PFS will be analyzed on the FAS for HCC subjects and Response Evaluable Set as appropriate.

The exact 95% confidence intervals of ORR will be calculated using Clopper-Pearson method. DOR and time to response will be for subjects who have achieved a best response of CR or PR only. Censoring rules for PFS will follow the FDA guidance and are specified in Table 5. PFS will be reported in both summary tables and plotted with Kaplan-Meier curve.

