# 8 DEFINITIONS AND CONVENTIONS FOR DATA HANDLING

The Baseline value will be defined as the last non-missing measurement prior to the first dose of the study drug. A Baseline value doesn't have to be collected in the Baseline period.

Descriptive statistics for continuous variables will be reported using number of non-missing measurements (n), mean, standard deviation (SD), median, the first quartile (Q1), the third quartile (Q3), minimum and maximum.

Descriptive statistics for categorical variables will be summarized as number (percentage) of subjects.

P-values will be presented with 3 decimal places or “< .001”, rates will be presented with 1 decimal place or 0, CIs of rates will be reported as two-sided and calculated using Clopper-Pearson method, and time-to-event variables will be estimated using Kaplan-Meier method.

Further definitions and conventions for data handling will be presented in “Programming Specifications”.

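### One limit in the ORR precision table is wrong: for 4 responders in 40 the exact 95% upper limit is 0.237, not 0.234

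*Protocol*

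**What the plan says.** For Part 2, the synopsis states that "a sample size of 40 evaluable subjects per dose schedule will be enrolled to examine QD and/or BID dosing of H3B-6527". It gives no null rate, target rate or power for this number. The numerical support is a table of intervals, introduced with the words "For a reference of the precision of ORR estimates, the associated 2-sided 95% CIs for ORR up to 30% for 40 subjects are provided". The table has eleven rows, from 2 responders (5%) to 12 responders (30%) in 40 subjects. It appears three times: in the synopsis under the sample size rationale, as Table 9 in Protocol Section 9.7.2, and as Table 4 in SAP Section 4. In all three, the row for 4 responders (10%) reads (0.028, 0.234).

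The Protocol does not name the interval method. The SAP does so twice. Section 5.4.1 says "The exact 95% confidence intervals of ORR will be calculated using Clopper-Pearson method", and Section 8 sets the same convention for rates in general: "CIs of rates will be reported as two-sided and calculated using Clopper-Pearson method".

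**The concern.** The upper limits should rise smoothly down the table, but the 10% row does not fit. The printed upper limits for 2 to 6 responders are 0.169, 0.204, 0.234, 0.268 and 0.298, so the successive steps are 0.035, 0.030, 0.034 and 0.030. A step that falls and then rises again points to a single wrong cell.

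Two things are at stake. First, the table is the only quantitative statement behind 40 subjects per schedule, and the error makes the precision look slightly better than it is at one of the low response rates the table covers. Second, if exactly 4 of 40 respond, the analysis run by the SAP's own method will give an upper limit of 23.7%, while the SAP's own table says 23.4%. A reader comparing the study report with the plan would find a difference that nothing explains.

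**Working it through.** **Inputs.** n = 40 per schedule (synopsis; Protocol 9.7.2; SAP 4). Two-sided 95%, so 0.025 in each tail (table titles). Responders x = 2 to 12 (table rows). Method: Clopper-Pearson (SAP 5.4.1 and 8).

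**Formula.** Lower limit = 0.025 quantile of Beta(x, n − x + 1). Upper limit = 0.975 quantile of Beta(x + 1, n − x).

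**Reproducing the table.**

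| x of 40 | Printed | Clopper-Pearson | Agrees to 3 decimals |
|---|---|---|---|
| 2 | 0.006, 0.169 | 0.00611, 0.16920 | both |
| 3 | 0.016, 0.204 | 0.01574, 0.20386 | both |
| **4** | **0.028, 0.234** | **0.02793, 0.23664** | **lower only** |
| 5 | 0.042, 0.268 | 0.04186, 0.26803 | both |
| 6 | 0.057, 0.298 | 0.05710, 0.29835 | both |
| 7 | 0.073, 0.328 | 0.07338, 0.32779 | both |
| 8 | 0.091, 0.356 | 0.09052, 0.35648 | both |
| 9 | 0.108, 0.385 | 0.10840, 0.38451 | both |
| 10 | 0.127, 0.412 | 0.12691, 0.41196 | both |
| 11 | 0.146, 0.439 | 0.14601, 0.43888 | both |
| 12 | 0.166, 0.465 | 0.16563, 0.46532 | both |

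Twenty-one of 22 limits agree, including the lower limit of the disputed row. For x = 4 the upper limit is the 0.975 quantile of Beta(5, 36) = 0.23664, which rounds to 0.237.

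**Direct check of the tail.** An exact upper limit p must satisfy P(X ≤ 4 | n = 40, p) = 0.025.
- At p = 0.234 the probability is 0.0272, which is too large, so the limit lies higher.
- At p = 0.2366 it is 0.0250, as required.

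**Could another method give the printed pair (0.028, 0.234)?** For 4 of 40:

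| Method | Interval |
|---|---|
| Wald | 0.0070, 0.1930 |
| Wilson | 0.0396, 0.2305 |
| Wilson with continuity correction | 0.0325, 0.2460 |
| Agresti-Coull | 0.0339, 0.2362 |
| Jeffreys | 0.0347, 0.2204 |
| Mid-P | 0.0326, 0.2238 |
| Inverted exact binomial test | 0.0349, 0.2348 |

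None does.

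**Could another n give it?** The Clopper-Pearson upper limit for 4 responders is 0.2422 at n = 39, 0.2366 at n = 40 and 0.2313 at n = 41. The printed 0.234 falls between n = 40 and n = 41, so no whole number of subjects produces it.

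**Size of the error.**
- Upper limit: 0.237 − 0.234 = 0.003 at table precision (0.23664 − 0.234 = 0.0026 unrounded).
- Width: 0.234 − 0.028 = 0.206 printed, against 0.237 − 0.028 = 0.209 correct. The understatement is 0.003 / 0.209 = 1.4% of the width.
- Steps after correction: 0.035, 0.033, 0.031 and 0.030, which now fall steadily.

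**The case against.** The strongest reply is that nothing depends on this cell. The error is 0.3 percentage points in one of 22 limits, and the lower limit in the row is right. The rows on either side are right, so a reader's impression of the precision at 40 subjects barely changes. ORR is a secondary endpoint for preliminary activity, and Part 2 also serves to characterise safety and tolerability (Protocol 9.1.1.2). The table is offered as a reference, and the documents do not say that 40 was derived from it. There is no formal interim analysis for efficacy, and the choice between once-daily and twice-daily dosing is a joint judgement on several kinds of data. The reported intervals will be computed from the data, so the study report would show the correct limit.

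All of this stands, and it settles the weight of the point: this is a minor correction. It does not make the printed number right.

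A narrower objection is that the Protocol names no interval method, so for its two tables Clopper-Pearson is an inference. That is true. But the inference is strong, because 21 of 22 limits match, and SAP Table 4 carries the same numbers alongside an explicit statement of the method. Nor is a fault in reading the PDF likely, since the same value appears in three separate tables across two documents.

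**Conclusion.** The point holds. For 4 responders in 40, the exact two-sided 95% interval is (0.028, 0.237), and the printed upper limit of 0.234 is 0.003 too low. One row of eleven is affected, and it is repeated in three tables. The most likely cause is a transcription slip carried from one document to the other, though the documents cannot confirm that.

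The conclusion assumes that all three tables are meant to be Clopper-Pearson intervals, as the SAP states and as the other 21 limits confirm. The 40 subjects per schedule, the conduct of the trial and the final analysis are unaffected. What is affected is the accuracy of the only quantitative support given for the Part 2 size, and the agreement between the SAP's table and the SAP's method.

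**What to change.** In the row for 4 responders in 40 (10%), replace (0.028, 0.234) with (0.028, 0.237) in the synopsis table, in Table 9 of Protocol Section 9.7.2 and in Table 4 of SAP Section 4. The other ten rows stay as they are. It would also help to name Clopper-Pearson in the title or footnote of the two Protocol tables, so that a reader can check them without the SAP.

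The cost is one number in three places, which can go into the next revision of each document. The stated precision for that row becomes slightly less favourable. Sample size, procedures and analysis programs do not change.
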